5.4. Final Analysis

5.4.1. Outcome Measures

For each participant, primary and secondary endpoints will be defined for each anatomical site and organism. [Primary source data: SAMPLE COLLECTION, STUDY COMPLETION and LAB DATA]

a. Primary Endpoints

Note: Derived datasets relating to the derivation of these endpoints will undergo independent results verification in accordance with CBAR PROG.10033.

Anatomic site infection status is determined by the reference standard (described in Section 4.2).

- o Infection status for Neisseria gonorrhoeae in the rectum as determined by each NAAT
- o Infection status for Neisseria gonorrhoeae in the pharynx as determined by each NAAT
- o Infection status for Chlamydia trachomatis in the rectum as determined by each NAAT
- o Infection status for Chlamydia trachomatis in the pharynx as determined by each NAAT

5.4.2. Final Analysis Considerations

Note: All dataset derivation programs for this endpoint will undergo independent results verification in accordance with CBAR PROG.10033; validation requirements for analysis programs are stated below.

As noted previously, for all final analyses, data collected from eCRFs or data entered by the laboratories in the laboratory information management system (LIMS) will be used. Data from additional sources such as machine data or issue tracking logs may be reviewed for clarification, but will not be used for analysis.

The result for each diagnostic test will be compared with the ASIS for that anatomic site and organism. PPA and NPA will also be estimated for each diagnostic test with 95% confidence intervals. Confidence intervals will be estimated using the Score method.⁸ If the test under consideration has "no result" because the test was not run and no attempt was made to test the sample, the test result will be excluded from primary analysis. If the ASIS result is invalid, this result will be excluded from the primary analysis.

FDA guidance documents will be followed as part of the primary analysis to incorporate indeterminate ASIS or test results for the test under consideration that are equivocal.⁹ It is recognized that there are pros and cons to the manner in which indeterminates are handled and how these impact the resulting estimates of PPA and NPA. The primary analysis approach is the most conservative and is biased downwards. If PPA is >90% under this scenario, then the conclusion of PPA >90% is clear.

Sensitivity analyses will be conducted as appropriate to evaluate the impact of diagnostic accuracy for a range of scenarios addressing indeterminate ASIS results. This will include counting indeterminate ASIS results against the results for the test under consideration with all combinations of Infected/Indeterminate/Not Infected with all outcomes from the test under consideration (Positive/Equivocal/Negative/No result or Invalid) evaluated. These analyses may not be conservative for calculations of PPA and NPA.

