6.0 Statistics

6.1 Study Design

This is a cross-sectional, single visit study to evaluate the diagnostic accuracy of NAATs for the detection of NG and CT from pharyngeal and rectal swab specimens. Study participants will have swabs collected from both the rectum and pharynx, following any specimens taken for clinically indicated testing. Each of the swabs from each anatomic location will be tested for both NG and CT using three different NAATs, with a 4th test collected and tested as a tiebreaker, if needed. [redacted] Diagnostic accuracy will be calculated with respect to an anatomic site infected status (ASIS) reference standard described in Section 3.5. As the reference standard is imperfect, we will report positive percent agreement and negative percent agreement in place of sensitivity and specificity.

One potential limitation of this study is that all three of the tests in the reference standard are NAATs. However, all three tests [redacted]. So while, theoretically, there may be correlation in the errors produced by the three tests, the varied molecular targets and the different methods of capture, amplification and detection should mitigate this concern.

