6.3 Sample Size

For each assay, PPA and NPA³⁵ will be estimated for each of three diagnostic tests defined by pathogen - anatomical site combinations:

- *Neisseria gonorrhoeae* in the rectum
- *Neisseria gonorrhoeae* in the pharynx
- *Chlamydia trachomatis* in the rectum
- *Chlamydia trachomatis* in the pharynx

Each pathogen/anatomic site combination will be evaluated by constructing 95% Score confidence interval estimates for PPA and NPA and evaluating whether 90% can be ruled out by the lower bound of the CI with reasonable confidence.

NPA is expected to be greater than PPA and there will be considerably more not-infected than infected anatomic site, implying that there will be greater power for evaluating NPA. Thus it will suffice to size the study to evaluate PPA.

Assuming that the true PPA is 96%,¹³ then 157, 174, and 196 evaluable participants that are infected are needed to have 80%, 85%, and 90% power respectively to demonstrate a PPA of greater than 90%. Since all of the participants will contribute to the evaluation of all three pathogen-anatomical site diagnostic tests, it will suffice to size the study for the diagnostic test with the lowest expected prevalence (except CT in the pharynx). The study will be more than sufficiently sized for more prevalent disease.

It is expected that the disease prevalence of NG in the rectum, NG in the pharynx, and CT in the rectum will each be greater than 7.5% in the population under evaluation.^{13,14,16-20} Table 3 summarizes the required number of participants to have 80% and 90% probabilities of obtaining the 157, 174, and 196 evaluable participants that are disease-positive to have 80%, 85%, and 90% power when the true prevalence of disease is 7.5%, 10%, and 12.5%.

Table 3: Sample size required number to have 80% and 90% probabilities of obtaining the 157, 174, and 196 evaluable participants that are disease-positive when the true prevalence of disease is 7.5%, 10%, and 12.5% in order to have 80%, 85%, and 90% power (two-sided alpha=0.05) to conclude that sensitivity is greater than 90% when the true sensitivity is 96%.

| Prevalence of Disease Positive | Power | Required Disease Positive to Obtain Power | Required Sample Size to have 80% probability of obtaining required Disease positive participants | Required Sample Size to have 90% probability of obtaining required Disease positive participants |
|--------------------------------|-------|---|--|--|
| 7.5% | 80% | 157 | 2250 | 2325 |

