- Additional sensitivity analyses, including the use of latent class models, will be explored. Details will be in the statistical analysis plan.

Table 5. Use of the ASIS in calculation of the positive and negative percent agreement for the Company 1 Assay (Company 1) and Company 3 Assay (NG only).

| | | ASIS | | |
|---|-----------------------|-----------------------|----------------|---------------|
| | | Infected | Indeterminate* | Not infected |
| Result of Test under Consideration** | Positive/Detected | A | C | E |
| | Negative/Not detected | B | D | F |
| | No result | Exclude from analysis | | |
| | PPA | $A / (A+B+D)$ | | |
| | NPA | | | $F / (C+E+F)$ |

*The middle, indeterminate column will be included in the analyses as “Infected” or “Not infected” as described in the sensitivity analyses below.

**Per the ASIS definition in Section 2.3

If the test under consideration has “no result” because the test was not run and no attempt was made to test the sample or because of invalid ASIS results it will be excluded from the primary analysis.

Comprehensive sensitivity analyses will be conducted. These include:

- Classify indeterminate tests on the basis of symptom status. Include indeterminate tests as Infected if the participant is symptomatic in that compartment. Include indeterminate tests as not infected in the participant is asymptomatic in that compartment.

- Include all indeterminate tests as infected
 - $PPA = (A+C) / (A+B+C+D)$
 - $NPA = F / (E+F)$
- Include all indeterminate tests as not infected
 - $PPA = A / (A+B)$
 - $NPA = (D+F) / (C+D+E+F)$
- Additional sensitivity analyses that consider indeterminate results as “missing” and utilize imputation strategies, and graphical techniques
- Additional sensitivity analyses, including the use of latent class models, will be explored. Details will be in the statistical analysis plan.

There are pros and cons to the manner in which indeterminates are handled and the resulting calculations of PPA and NPA. The primary definition is the most conservative but is biased downwards. If $PPA > 90\%$ under this scenario, then the conclusion of $PPA > 90\%$ is clear. The second and third sensitivity analyses count indeterminates (treat all as infected or not infected, respectively) but may not be conservative for calculations of PPA and NPA.

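### The SAP omits the latent class analysis that the protocol deferred to it, so no planned analysis can show how errors shared by the NAATs affect PPA

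*SAP*

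**What the plan says.** Each assay is judged against an anatomic site infection status (ASIS) built from the other two NAATs. A NAAT tiebreaker is added when those two disagree, and two of three decide (Protocol 2.3, SAP 5.2). Protocol 6.1 names the all-NAAT reference as a limitation and grants that "theoretically, there may be correlation in the errors produced by the three tests". It argues that different targets and methods should lessen the problem, and reports PPA and NPA rather than sensitivity and specificity because the reference is imperfect.

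The criterion in Protocol 6.3 is "evaluating whether 90% can be ruled out by the lower bound of the CI". The text there works with PPA, but the title of Table 3 speaks of power "to conclude that sensitivity is greater than 90% when the true sensitivity is 96" percent.

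On indeterminate ASIS results, SAP 5.4.2 states: "The primary analysis approach is the most conservative and is biased downwards. If PPA is >90% under this scenario, then the conclusion of PPA >90%", a conclusion it then calls clear. Protocol 6.6.1 says much the same. Protocol 6.6.1 also says, once for each group of assays: "Additional sensitivity analyses, including the use of latent class models, will be explored. Details will be in the statistical analysis plan".

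**The concern.** An infected site that the reference NAATs miss is classed as Not infected. If the assay under study misses it too, that miss is counted as agreement in the NPA and never reaches the PPA denominator. Low organism load at a site is one way all the swabs could fail together, and different molecular targets would not remove it.

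A latent class model is the only analysis named in the protocol that does not take the ASIS as truth. Without it, a report intended to support clearance has no result that bears on shared errors. Its text would call the primary approach conservative without saying in what respect.

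**Working it through.** **1. What each planned analysis changes.** SAP Tables 12 and 14 list four scenarios besides the primary analysis: indeterminates classified by symptoms, all as infected, all as not infected, or treated as missing together with equivocals and modelled. Figure (h) in SAP 5.4.3 varies the share of indeterminates taken as positive. All of these move indeterminate or equivocal cells. A site already classed Infected or Not infected by the NAATs stays there. The SAP contains no latent class model, and its list of revisions does not mention removing one.

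**2. The plan's own figure.** With a null value of 90%, a true PPA of 96% and two-sided alpha of 0.05 (Protocol 6.3):

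n = (1.96·√(0.90·0.10) + z_power·√(0.96·0.04))² / 0.06²

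This gives 157.5, 173.8 and 195.6 for 80%, 85% and 90% power, matching the stated 157, 174 and 196. At n = 157 the Score lower bound is 90.3% with 149 positives and 89.5% with 148, so a pass needs at least 149. If PPA is exactly 90%, the exact binomial chance of a pass is 2.1%.

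**3. PPA against sensitivity.** The documents give no organism-load data, so these inputs are assumed: detection is 99% at ordinary infected sites and 50% at low-load sites, 20% of infected sites are low-load, tests are independent given load, and false positives are independent. Prevalence is 7.5%, the protocol's planning floor. Indeterminates are ignored.

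The chance that the reference calls a site infected, when each test is positive with probability s, is a(s) = s² + 2s²(1−s). So a(0.99) = 0.9997 and a(0.5) = 0.5.

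- Sensitivity = 0.8·0.99 + 0.2·0.5 = 89.2%.
- PPA at specificity 100% = (0.8·0.9997·0.99 + 0.2·0.5·0.5) / (0.8·0.9997 + 0.2·0.5) = 0.8418/0.8998 = 93.6%.
- With q = 1 − specificity, PPA = [0.075·0.8418 + 0.925·a(q)·q] / [0.075·0.8998 + 0.925·a(q)]. At specificity 95%, a(0.05) = 0.00725 and, with unrounded inputs, PPA = 0.0634676/0.0741884 = 85.5%.

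| Specificity | PPA | PPA minus sensitivity (points) | Chance of a pass, n = 157 |
|---|---|---|---|
| 100% | 93.6% | +4.4 | 31% |
| 99% | 93.2% | +4.0 | 25% |
| 97% | 90.4% | +1.2 | 3% |
| 95% | 85.5% | −3.7 | about 0% |

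With 10% low-load sites (sensitivity 94.1%) the gap is +2.3 points at specificity 100% and −0.8 at 97%. With 5% it is +1.2 at 100% and −0.2 at 98%. Stronger dependence widens it: with 10% low-load sites detected 10% of the time, and 98% detection elsewhere, sensitivity is again 89.2%. PPA at specificity 100% is then 97.7%, with a 99% chance of a pass.

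**4. Whether the primary PPA is the lowest for indeterminates.** For the assays in SAP Table 12 the primary PPA is A/(A+B+C+F). Counting all indeterminates as infected gives (A+D)/(A+B+C+D+E+F). The second is lower whenever D·(B+C+F) < A·E, which can happen because the primary formula leaves out cell E (equivocal test, indeterminate ASIS).

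Illustrative counts A=147, B=1, C=5, D=0, E=6, F=2:

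- Primary: 147/155 = 94.8%, lower bound 90.1%, a pass.
- All indeterminates as infected: 147/161 = 91.3%, lower bound 85.9%, a fail.

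For the assays in SAP Table 14 there is no equivocal row, and A/(A+B+D) cannot exceed the result of either all-infected or all-not-infected counting.

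**The case against.** A reader might infer that the plan presents PPA as a lower bound on sensitivity, or that the primary PPA is simply biased upwards. The documents support neither. In both places the remark on downward bias follows a sentence about handling indeterminates, and the conclusion drawn is about PPA. Protocol 6.1 discloses the all-NAAT limitation and chooses PPA for that reason. As agreement with the ASIS, PPA is not biased by shared misses; they only separate it from sensitivity. The word sensitivity in the Table 3 title is a labelling slip.

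The direction of the gap is not fixed either. Protocol 1.2 cites NG specificities of 72–100% in the pharynx and 95–100% in the rectum, and the table above changes sign within the rectal range. The low-load inputs are assumed. In the 5% and 10% low-load cases true sensitivity is above 90%, so concluding that it exceeds 90% would be correct.

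A latent class model also has limits. Three binary tests give 2³ − 1 = 7 free cell probabilities. Three sensitivities, three specificities and one prevalence use all seven, leaving nothing with which to estimate dependence. Letting prevalence vary by clinic helps only if accuracy is constant across clinics.

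These points stand, and they limit what the analysis can deliver. They do not explain its absence. The protocol's commitment to explore is soft, but its commitment to put the details in the SAP is plain. Nor can the penalty for indeterminates be relied on to offset shared misses. Pulling a PPA of 96% down to 90% with 157 infected takes 157·(0.96/0.90 − 1) = 10.5 test-negative indeterminates, and under the ASIS table these arise only when a comparator or tiebreaker is equivocal or has no result.

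**Conclusion.** The concern holds in a limited form. An analysis deferred to the SAP is missing without explanation, and nothing else planned can show the effect of errors shared by the NAATs. PPA may lie above or below sensitivity: in the main illustration, from 4.4 points above to 3.7 below as specificity falls from 100% to 95%. These sizes rest on the assumed low-load share and detection rates, 7.5% prevalence and independent false positives; they show possible scale and are not estimates for these assays. The primary PPA as defined is unaffected. The conservative label is sound for indeterminates in the Table 14 assays but not guaranteed for the Table 12 assays.

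**What to change.** 1. In SAP 5.4.2 and Protocol 6.6.1, limit the statement to the handling of indeterminates. For the Table 12 assays, either drop the claim that the primary approach is the most conservative or also report the lowest PPA across the indeterminate scenarios. Add that PPA can lie above or below sensitivity because of correlated errors or false positives in the reference. Correct the Table 3 title to PPA at the same time; that change is clerical.
2. In SAP 5.4.3, add the deferred latent class analysis as a secondary sensitivity analysis for each organism and site. Allow imperfect specificity, and report sensitivity over a prespecified range of between-test dependence rather than as a single estimate. A model that assumes conditional independence would not address the concern.

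The cost is a few sentences and one secondary model on data already held; the sample size and primary analysis do not change. The drawback is that the result depends on the assumed dependence, which three binary tests cannot identify, and it may be less favourable than PPA.

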5.4.3. Primary Analyses

The following will be conducted for the three diagnostic tests.

Note: Analysis programs will require independent results verification per CBAR PROG.10033.

 Table: For each diagnostic assay (including the tiebreaker assay), frequency of observed test outcomes by anatomical site and organism combination. [See Table 8 described in Section 5.3.2; data source: LAB DATA]

⁸ FDA. Establishing the performance characteristics of in vivo diagnostics devices for Chlamydia trachomatis and/or Neisseria gonorrhoeae: screening and diagnostic testing. (2011).

⁹ FDA. Establishing the performance characteristics of in vivo diagnostics devices for Chlamydia trachomatis and/or Neisseria gonorrhoeae: screening and diagnostic testing. (2011).

- b. Table: Frequency (%) of re-tests by clinic and platform. This will be conducted for each test under consideration and be presented by anatomical site and organism combination. [Data source: LAB DATA; DEMOG]
- c. Table: Listing and frequency (%) of re-tests results by platform. This will be conducted for each test under consideration and be presented by anatomical site and organism combination. [Data source: LAB DATA]
- d. Table/Figure: Frequency of comparator NAAT result and tiebreaker result combinations to define ASIS. This will be conducted for each test under consideration and be presented by anatomical site and organism combination. There will be a total of three tables to reflect the three tests under consideration. [See **Table 9** previously described in in Section 5.3.2; data source: LAB DATA]
- e. Table/Figure: Number (%) of observed total test results, ASIS results, and prevalence (i.e., infection) rate. This will be conducted for each test under consideration and be presented by anatomical site and organism combination. [See **Table 10** previously described in Section 5.3.2; data source: LAB DATA]
- f. Table: Observed infection rate by clinic. This will be conducted for each test under consideration and be presented by anatomical site and organism combination. [Data source: LAB DATA; DEMOG]
- g. Tables:
 - Cross comparison of number (%) of results of test under consideration versus ASIS;
 - Estimates of PPA and NPA with 95% Score confidence intervals;
 - Due to differences in PPA and NPA calculations for NAAT platforms that do not have an [redacted] result when it is the test under consideration, analysis results will be estimated and presented separately based on this distinction as follows:
 - Table 11 and Table 12: Company 2 Assay (Company 2) and Company 3 Assay (Company 3).
 - Table 13 and Table 14: Company 1 Assay (Company 1) and Company 3 Assay (Company 3).
- h. Figure: Plot of PPA and 95% confidence interval band versus proportion of indeterminate ASIS results assumed to be positive (range of 0 to 1); vice-versa for NPA plot.
- i. Table: Using Fischer's exact test, the association between test results and randomized swab order will be examined. Associations will be conducted by anatomical site and organism combination.

Table 11: Result of Test under Consideration versus ASIS: Company 2 Assay (Company 2) and Company 3 Assay (Company 3)

		ASIS			
		Infected	Indeterminate	Not infected	
	Positive	A	D	G	
Result of Test under Consideration	Equivocal	В	E	Н	
	Negative	С	F	I	
	No result	Exclude from analysis ¹			
¹ Note: If the test under consideration has "no result" because the test was not run and no attempt was made to test the sample, the					

test result will be excluded from primary analysis. If the ASIS result is invalid, this result will be excluded from the primary analysis.

Table 12: Calculation of the positive and negative percent agreement: Company 2 Assay (Company 2) and Company 3 Assay (Company 3)

Analysis Type	PPA	NPA		
Primary Analysis	A / (A+B+C +F)	l / (G+H+l + D)		
Sensitivity Analysis Scenarios				
Classify indeterminates ¹ using symptom status reported	A / (A+B+C+F)	I / (G+H+I+D)		
from [SIGNS AND SYMPTOMS]				
Include all indeterminate tests as infected.	(A+D) / (A+B+C+D+E+F)	l / (G+H+I)		
Include all indeterminate tests as not infected.	A / (A+B+C)	(I+F) / (D+E+F+G+H+I)		
Consider indeterminate and equivocal test results as "missing", with the assumption of missing at random, and model the missing results. ²	A / (A+C)	l / (G+l)		
Classify indeterminate tests on the basis of symptom status. Include indeterminate tests as Infected if the participant is symptomatic in that compartment; include indeterminate tests as not infected in the participant is asymptomatic in that compartment. Cells B, D, E, F and H will be assigned or weighted to cells A, C, G and I based on modeling of the missing results.				

Table 13: Result of Test under Consideration versus ASIS: Company 1 Assay (Company 1) and Company 3 Assay (Company 3)

		ASIS			
		Infected	Indeterminate	Not infected	
	Positive/Detected	A	С	E	
Result of Test under Consideration	Negative/Not detected	В	D	F	
	No result	Exclude from analysis ¹			
Note: If the test under consideration has "no result" because the test was not run and no attempt was made to test the sample, the					

¹ Note: If the test under consideration has "no result" because the test was not run and no attempt was made to test the sample, the test result will be excluded from primary analysis. If the ASIS result is invalid, this result will be excluded from the primary analysis.

Table 14: Calculation of the positive and negative percent agreement: Company 1 Assay (Company 1) and for the Company 3 Assay (Company 3)

Analysis Type	PPA	NPA
Primary Analysis	A / (A+B +D)	F / (C+E +F)
Sensitivity Analysis Scenarios		
Classify indeterminates ¹ using symptom status reported from [SIGNS AND SYMPTOMS]	A / (A+B+D)	F / (C+E+F)
Include all indeterminate tests as infected.	(A+C) / (A+B+C+D)	F / (E+F)
Include all indeterminate tests as not infected.	A / (A+B)	(D+F) / (C+D+E+F)
Consider indeterminate and equivocal test results as "missing", with the assumption of missing at random, and model the missing results. ²	A / (A+B)	F / (E+F)

¹ Classify indeterminate tests on the basis of symptom status. Include indeterminate tests as Infected if the participant is symptomatic in that compartment; include indeterminate tests as not infected in the participant is asymptomatic in that compartment.
² Cells C and D will be assigned or weighted to cells A, B, E and F based on modeling of the missing results.

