3.0 Study Design

3.1 Study Design

This will be a cross-sectional, single visit study evaluating the performance of three commercial NAATs to detect NG and CT in the rectum and pharynx.^{1,2,32,33} A fourth NAAT is being used as a tiebreaker.^{26,27} We are not evaluating the performance of this fourth NAAT.

The study will include specimens collected from adult subjects seeking sexually transmitted disease (STD) testing at the participating clinics, which include clinics focused on sexually transmitted diseases, women's health, student health, family planning clinics, and clinics specializing in lesbian, gay, bisexual, and transgender (LGBT) health. Potential subjects will be identified, assessed for eligibility and approached for informed consent. Both symptomatic and asymptomatic individuals will be included in the study population.

The study will enroll up to 3,000 subjects who will have four pharyngeal and four rectal swabs collected as part of a one-time study visit. Each manufacturer will have specific collection kit and transport media. Additional data collection will include, but is not limited to, eligibility screening questions, gender, age, and patient report of relevant pharyngeal, rectal, or other relevant symptoms, and swab collection completeness. Subjects will be classified as symptomatic or asymptomatic for each anatomic site. Results of testing at other anatomic sites and results of clinical testing will not be available.

Each swab will be used for a specific NAAT, which will be run at one of the two reference testing laboratories. The ASIS will be defined by the results of the two other nucleic acid amplification tests, and a tiebreaker test (if necessary), as shown in Table 2. Each anatomic site will be considered in isolation.

When accrual is complete, the study will be closed and an analysis plan will be enacted to finalize the database for analysis.

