4.3 Enrollment

Once enrolled, eight swabs will be taken: four swabs will be taken from the pharynx and four swabs will be taken from the rectum in addition to any swabs taken as part of routine clinical care. The swabs collected for routine clinical care will be taken first. The order of the research swabs will be randomized per subject to account for the possibility that the yield of the swab is affected by previous swabs at the same anatomic site. The swabs will be stored and transported per manufacturer guidelines. Results of those NAATs will not be reported back to the treating clinician for clinical purposes.

Data collection will include, but is not limited to, assessment of signs and symptoms of rectal and/or pharyngeal infection, as well as socio-demographic information such as age (not date of birth), race, ethnicity and gender, and swab collection completeness.

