6.4 Randomization of Swabs

Randomization will be employed to ensure that the swab order distribution is the same for 4 tests, the three NAATs under investigation in the study and the tiebreaker test. SAS software (Cary, NC) will be used to generate permuted blocks with a block size of 24, to ensure that each NAAT and the tiebreaker test would have their swab distributions consisting of 1/4 being first swabs, 1/4 being second swabs, 1/4 being third swabs and 1/4 being fourth swabs.

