+	+	Not indicated	Infected	XX
+	-	+	Infected	XX
(Remaining observed combination	ns as described in Table 4 .)		
Anatomical Site and Organism	n: CT, throat			
Comparator NAAT Result 1	Comparator NAAT Result 2	Tiebreaker NAAT result	ASIS	Frequency (n)
+	+	Not indicated	Infected	XX
+	-	+	Infected	XX
(Remaining observed combinations as described in Table 4 .)				

c. Table/Figure: Number (%) of observed total test results, ASIS results, and prevalence (i.e., infection) rate. This will be conducted for each test under consideration and be presented by anatomical site and organism combination as shown in **Table 10** below. [Data source: LAB DATA]

Table 10: Number (%) of observed total test results, ASIS results, and prevalence (i.e., infection) rate for each test under consideration by anatomical site and organism

Test under con	Test under consideration: Company 1 System							
	Comparator NAATs: Company 2 and Company 3 Systems							
Tiebreaker NA	AT: Tiebre	aker Syster	m					
	Sample	Size (N)		AS	SIS		Prevalence	
	N	. ,					(P,	%) P
	(ITD)	N (mITD)	Infected	Not infected	Indeterminate	Invalid	(ITD)	(mITD)
NG, rectum								
NG, throat								
CT, rectum								
CT, throat								
Test under con								
			d Company 3 Sy	rstems				
Tiebreaker NA	AT: Tiebre	aker Systei	m					
	Sample	Size (N)		AS	SIS		Prevalence (P, %)	
	N (ITD)	N (mITD)	Infected	Not infected	Indeterminate	Invalid	P (ITD)	P (mITD)
NG, rectum								
NG, throat								
CT, rectum								
CT, throat								
Test under con								
			d Company 2 Sy	vstems				
Tiebreaker NA	AT: Tiebre	aker Syste	m					
	Sample	Size (N)	ASIS			Preva (P,	llence %)	
	N (ITD)	N (mITD)	Infected	Not infected	Indeterminate	Invalid	P (ITD)	P (mITD)
NG, rectum								
NG, throat								
CT, rectum								
CT, throat								

- a. Table/Figure: Predicted infection rate summary for range of scenarios (see **Table 6** and **Table 7** described in Section 5.3.1).
- b. Table: Observed frequency of tiebreaker run versus expected number of runs (number, %).

c. Table: Using Fischer's exact test, the association between of test results and randomized swab order will be examined. Associations will be conducted by anatomical site and organism combination.

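### The swab-order test in SAP 5.4.3(i) is not restricted to infected sites and no PPA by swab position is planned, so a non-significant result would say little about loss of yield

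*SAP*

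**What the plan says.** Protocol 4.3 gives the reason for randomising. The order of the research swabs is "randomized per subject to account for the possibility that the yield of the swab is affected by previous swabs at the same anatomic site". The same section adds: "The swabs collected for routine clinical care will be taken first". Protocol 6.4 gives the method, permuted blocks of 24, and the aim: "Randomization will be employed to ensure that the swab order distribution is the same for 4 tests".

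The order effect is examined in two places, both in the SAP. The last item of 5.3.2 (interim) says that by Fisher's exact test "the association between of test results and randomized swab order will be examined". Item (i) of 5.4.3 (final) repeats this: "the association between test results and randomized swab order will be examined". Each is done by anatomical site and organism. The 5.4.3 list opens with "The following will be conducted for the three diagnostic tests", so the natural reading is one test per assay. Neither item limits the test to sites that the ASIS calls infected.

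PPA and NPA are planned overall (SAP 5.4.3) and by sex and symptom status (SAP 5.4.5), not by swab position. Protocol 6.6 has no swab-order analysis.

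**The concern.** A loss of yield can appear only where there is organism to collect. At 7.5% prevalence about 92.5% of sites are uninfected, and they are nearly all negative at every position. The number of positives at a position then depends mainly on how many infected people had that assay's swab there, which is chance. A drop in sensitivity of several points is small beside that variation.

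What is at stake is interpretation. If an assay's PPA is disappointing, the sponsor will want to know whether later swabs performed worse. A non-significant item (i) could be taken as reassurance that they did not, which it could hardly give. The ASIS needed for a sharper comparison is already derived for every site.

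**Working it through.** **Inputs from the documents**
- Enrolment up to 3,000 (Protocol synopsis), less 167 excluded (SAP Section D): 3,000 − 167 = 2,833, a ceiling.
- Each test is at each position a quarter of the time (Protocol 6.4): 2,833/4 = 708.25 results per position per assay.
- Prevalence: Protocol 6.3 expects that rectal NG, pharyngeal NG and rectal CT "will each be greater than 7.5% in the population under evaluation". Its Table 3 uses 7.5%, 10% and 12.5%.
- Design PPA 96%, to exclude 90%, two-sided alpha 0.05 (Protocol 6.3).

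**Assumptions**
- Specificity 99.5%, alpha 0.05 for the order test, and 96% sensitivity at swab 1.
- Linear losses of 6, 10 or 16 points by swab 4.

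**The plan's own figures.** n = [1.96·√(0.9·0.1) + z·√(0.96·0.04)]²/0.06² gives 157.5, 173.8 and 195.6 for 80%, 85% and 90% power. The plan states 157, 174 and 196. It gives no power for the order test.

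**Planned test, all sites.** P(positive at position j) = π·s_j + (1−π)(1−spec). For π = 7.5% and a 6-point loss:
- The probabilities are 0.0766, 0.0751, 0.0736 and 0.0721, or 54.3, 53.2, 52.1 and 51.1 expected positives.
- The first-to-fourth difference is about 3. The standard deviation of one count is √(708.25·0.0744·0.9256) ≈ 7.
- The noncentrality is λ = n·Σ(p_j − p̄)²/[p̄(1−p̄)] = 708.25·0.00001125/0.06884 = 0.116 on 3 df, so power is 5.7%.

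For 10 and 16 points, λ is 0.328 and 0.863.

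| Planned test, linear loss | 6 points | 10 points | 16 points |
|---|---|---|---|
| 7.5% prevalence | 5.7% | 7.0% | 10.6% |
| 12.5% prevalence | 6.3% | 8.7% | 15.7% |

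Exact Fisher power at 7.5% with specificity 100% is 5.7%, 7.1% and 10.9%. Reaching 80% power takes a linear loss of about 52 points at 7.5% and 40 points at 12.5%.

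**Other scenarios and readings**
- 96% as the average over positions (99, 97, 95, 93%): λ = 0.113 at 7.5%, power about 6%.
- Loss at swab 4 only: 6% to 12% at 7.5%, and up to 19% at 12.5%.
- Loss of 16 points after swab 2 at 12.5%, the highest found for other loss shapes: 25% to 27%.
- Order read as the 24 sequences: 5% to 8%. Three assays pooled on all sites: under 1% to 27%.

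**Infected sites only, 7.5% prevalence.** Infected sites per position: 0.075·708.25 = 53.1. λ = 53.1·Σ(s_j − s̄)²/[s̄(1−s̄)]:
- 6 points: 53.1·0.002/0.0651 = 1.63
- 10 points: 53.1·0.005556/0.0819 = 3.60
- 16 points: 53.1·0.014222/0.1056 = 7.15

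With a linear loss the trend test has the same λ on 1 df instead of 3.

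| Infected sites, per assay | 6 points | 10 points | 16 points |
|---|---|---|---|
| Unordered, 3 df | 16% | 33% | 60% |
| Trend, 1 df | 25% | 47% | 76% |

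Simulation gives 15%, 31% and 61% for the unordered test and 24%, 48% and 78% for trend. For the 99-to-93% case, λ = 53.1·0.002/0.0384 = 2.77, which gives about 25% unordered and 38% for trend.

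**The case against.** Order effects are handled by design. Randomisation places each test equally often at each position. No objective, endpoint or decision rule concerns yield by position. This stands, and it is why the severity is low.

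The loss sizes are assumed. Protocol 6.3 assumes 96% overall, not at swab 1. Losses of 6, 10 and 16 points from 96% imply averages of 93%, 91% and 88%, and the last is below the 90% to be exceeded. This stands as a limit on the scenarios. Keeping the average at 96% does not rescue the planned test: its power is then about 6%.

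The replacement is also underpowered for small losses, at about 25% for 6 points. This stands too. The case for the change rests on estimates by position with intervals, and on a better test from the same data.

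The all-sites reading comes from the absence of any restriction in the text. It is the natural reading, but item (i) states no denominator.

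Two stronger readings are tempting, and the documents support neither. A reader might infer that the planned test is invalid; read per assay it is valid but insensitive. A reader might infer that PPA and NPA, or the comparison between assays, are biased. Balanced order keeps that comparison fair, and nothing in item (i) enters the PPA or NPA formulas in SAP Tables 12 and 14.

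**Conclusion.** The concern holds as a low-severity point about what item (i) can conclude. With at most 2,833 participants, 96% sensitivity at swab 1, specificity 99.5% and linear losses of 6 to 16 points, the planned per-assay test has about 6% to 11% power at 7.5% prevalence and 6% to 16% at 12.5%. Fewer participants would lower this. A non-significant table would therefore not show that order is harmless. Restricting to ASIS-infected sites and testing for trend raises power at 7.5% to about 25%, 47% and 76%. These figures treat the ASIS as the true status.

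The change affects interpretation only: PPA, NPA and the conclusion about 90% stay as they are. Because routine-care swabs come first, research position 1 need not be the first swab at the site, so even the improved analysis describes loss across the research swabs.

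**What to change.** In SAP 5.4.3(i), for the final analysis only:

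- Keep the per-assay, all-sites table of every result category by randomised position. It remains useful for equivocal and failed tests: power is about 66% if failures rise linearly from an assumed 1% to 3%.
- Add, per assay and among sites infected by that assay's own ASIS, PPA by randomised position 1 to 4 with 95% Score intervals. Use A/(A+B+C) from Table 12, so that an equivocal counts as a miss, and A/(A+B) from Table 14.
- Add a trend test of misses across position.
- Repeat by actual collection position as a sensitivity check, since SAP 3.1 keeps swabs taken out of assigned order.
- State that a non-significant result is not evidence of no order effect.
- Treat pharyngeal CT as descriptive, since SAP 5.3.1 expects it to be rare.

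A test combining the assays is optional. It gains only if they share the loss, which cannot be assumed: "Each manufacturer will have specific collection kit and transport media".

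Keep the interim item in 5.3.2 as an all-sites table, stated as per assay, so that PPAs stay unreviewed during the study.

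The cost is SAP wording and a little more analysis of data already collected. Estimates by position will be imprecise: with about 53 infected sites per position at 7.5% prevalence, 48 of 53 detected gives a 95% Score interval of 80% to 96%.
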